**6.5.2. Dose modification and toxicity management for immune-related AEs associated with pembrolizumab**

AEs associated with pembrolizumab combination exposure, including coadministration with additional compounds, may represent an immune-related response. These immune related AEs (irAEs) may occur shortly after the first dose or several months after the last dose of pembrolizumab combination treatment and may affect more than one body system simultaneously. Therefore, early recognition and initiation of treatment is critical to reduce complications. Based on existing clinical study data, most irAEs were reversible and could be managed with interruptions of pembrolizumab combination treatment, administration of corticosteroids and/or other supportive care. For suspected irAEs, ensure adequate evaluation to confirm etiology or exclude other causes.

Additional procedures or tests such as bronchoscopy, endoscopy, skin biopsy may be included as part of the evaluation. Dose modification and toxicity management guidelines for irAEs associated with pembrolizumab are provided in [Table 5](#).

***Attribution of Toxicity:***

When study interventions are administered in combination, attribution of an adverse event to a single component is likely to be difficult. Therefore, while the investigator may attribute a toxicity event to the combination, to belantamab mafodotin alone, or to pembrolizumab alone, for adverse events listed in [Table 5](#), both interventions must be held according to the criteria in [[Table 5](#)].

***Holding Study Interventions:***

When study interventions are administered in combination, if the AE is considered immune-related, both interventions should be held according to recommended dose modifications.

***Restarting Study Interventions:***

Subjects may not have any dose modifications (no change in dose or schedule) of pembrolizumab in this study, as described in [Table 5](#). If the toxicity does not resolve or the criteria for resuming treatment are not met, the subject must be discontinued from all study interventions. If the toxicities do resolve and conditions are aligned with what is defined in [Table 5](#), the combination of belantamab mafodotin and pembrolizumab may be restarted at the discretion of the investigator.

**Table 5 Dose Modification Guidelines for Pembrolizumab-Related Adverse Events**

General instructions:				

 
1. Severe and life-threatening irAEs, should be treated with IV corticosteroids followed by oral steroids. Other immunosuppressive treatment should begin if the irAEs are not controlled by corticosteroids.
 
2. Pembrolizumab must be permanently discontinued if AE does not resolve or the corticosteroid dose is <math>\leq 10</math> mg/day within 12 weeks of the last pembrolizumab treatment.
 
3. The corticosteroid taper should begin when the irAE is <math>\leq</math>Grade 1 and continue at least 4 weeks.
 
4. If pembrolizumab has been withheld, pembrolizumab may resume after the irAE decreased to <math>\leq</math>Grade 1 after corticosteroid taper.
 
				

Immune-related AEs	Toxicity grade or conditions (CTCAEv4.03)	Action taken to pembrolizumab	irAE management with corticosteroid and/or other therapies	Monitor and follow-up
Pneumonitis	Grade 2	Withhold	
 
• Administer corticosteroids (initial dose of 1 to 2 mg/kg prednisone or equivalent) followed by taper
 
• Add prophylactic antibiotics for opportunistic infections
 
	
 
• Monitor subjects for signs and symptoms of pneumonitis
 
• Evaluate subjects with suspected pneumonitis with radiographic imaging and initiate corticosteroid treatment
 
• 
 

	Recurrent Grade 2, Grade 3 or 4	Permanently discontinue		
Diarrhea / colitis	Grade 2 or 3	Withhold	
 
• Administer corticosteroids (initial dose of 1 to 2 mg/kg prednisone or equivalent) followed by taper
 
	
 
• Monitor subjects for signs and symptoms of enterocolitis (i.e. diarrhea, abdominal pain, blood or mucus in stool with or without fever) and of bowel perforation (i.e. peritoneal signs and ileus).
 
• Subjects with <math>\geq</math> Grade 2 diarrhea suspecting colitis should consider GI consultation and performing endoscopy to rule out colitis.
 
• Subjects with diarrhea/colitis should be advised to drink liberal quantities of clear fluids. If
 

	Recurrent Grade 3 or Grade 4	Permanently discontinue		

Immune-related AEs	Toxicity grade or conditions (CTCAEv4.03)	Action taken to pembrolizumab	irAE management with corticosteroid and/or other therapies	Monitor and follow-up
				sufficient oral fluid intake is not feasible, fluid and electrolytes should be substituted via IV infusion.
AST / ALT elevation or Increased Bilirubin	Grade 2 	Withhold	
 
Administer corticosteroids (initial dose of 0.5 to 1 mg/kg prednisone or equivalent) followed by taper
 
	
 
Monitor with liver function tests (consider weekly or more frequently until liver enzyme value returned to baseline or is stable)
 

	Grade 3  or 4 	Permanently discontinue	
 
Administer corticosteroids (initial dose of 1 to 2 mg/kg prednisone or equivalent) followed by taper
 
	
Type 1 diabetes mellitus (T1DM) or Hyperglycemia	New onset T1DM or Grade 3 or 4 hyperglycemia associated with evidence of $\beta$ -cell failure	Withhold 	
 
Initiate insulin replacement therapy for subjects with T1DM
 
Administer an antihyperglycemic in subjects with hyperglycemia
 
	
 
Monitor subjects for hyperglycemia or other signs and symptoms of diabetes.
 

Hypophysitis	Grade 2	Withhold	
 
Administer corticosteroids and initiate hormonal replacements as clinically indicated.
 
	
 
Monitor for signs and symptoms of hypophysitis (including hypopituitarism and adrenal insufficiency)
 

	Grade 3 or 4	Withhold or permanently discontinue 		
Hyperthyroidism	Grade 2	Continue	
 
Treat with nonselective beta-blockers (e.g. propranolol) or thionamides as appropriate
 
	
 
Monitor for signs and symptoms of thyroid disorders.
 

	Grade 3 or 4	Withhold or Permanently discontinue 		

Immune-related AEs	Toxicity grade or conditions (CTCAEv4.03)	Action taken to pembrolizumab	irAE management with corticosteroid and/or other therapies	Monitor and follow-up
Hypothyroidism	Grade 2, 3 or 4	Continue	
 
Initiate thyroid replacement hormones (e.g. levothyroxine or liothyroinine) per standard of care
 
	
 
Monitor for signs and symptoms of thyroid disorders.
 

Nephritis; grading according to increased creatinine or acute kidney injury	Grade 2	Withhold	
 
Administer corticosteroids (prednisone 1 to 2 mg/kg or equivalent) followed by taper.
 
	
 
Monitor changes of renal function
 

	Grade 3 or 4	Permanently discontinue		
Neurological Toxicities	Grade 2	Withhold	Based on severity of AE administer corticosteroids	Ensure adequate evaluation to confirm etiology, and/or exclude other causes
	Grade 3 or 4	Permanently discontinue		
Myocarditis	Asymptomatic cardiac enzyme elevation with clinical suspicion of myocarditis (previously CTCAE v4.0 Grade 1)	Withhold	
 
Based on severity of AE administer corticosteroids
 
	
 
Ensure adequate evaluation to confirm etiology or exclude other causes
 

	Grade 2, 3 or 4	Permanently discontinue		
Exfoliative Dermatologic Conditions	Suspected SJS, TEN, or DRESS	Withhold	Based on severity of AE administer corticosteroids	Ensure adequate evaluation to confirm etiology, or exclude other causes
	Confirmed SJS, TEN, or DRESS	Permanently discontinue		
All Other irAEs	Persistent Grade 2	Withhold	
 
Based on severity of AE administer corticosteroids
 
	
 
Ensure adequate evaluation to confirm etiology or exclude other causes
 

Immune-related AEs	Toxicity grade or conditions (CTCAEv4.03)	Action taken to pembrolizumab	irAE management with corticosteroid and/or other therapies	Monitor and follow-up
	Grade 3	Withhold or discontinue based on event  .		
	Recurrent Grade 4 or Grade 4	Permanently discontinue		

AE(s)=adverse event(s); ALT=alanine aminotransferase; AST=aspartate aminotransferase; CTCAE=Common Terminology Criteria for Adverse Events; DRESS=Drug Rash with Eosinophilia and Systemic Symptom; GI=gastrointestinal; ir=immune related; IV=intravenous; SJS=Stevens-Johnson Syndrome; T1DM=type 1 diabetes mellitus; TEN=Toxic Epidermal Necrolysis; ULN=upper limit of normal.

[figure not shown]
NOTES: Non-irAE will be managed as appropriate, following clinical practice recommendations.

1. AST/ALT: >3.0 - 5.0 x ULN if baseline normal; >3.0 - 5.0 x baseline, if baseline abnormal; bilirubin:>1.5 - 3.0 x ULN if baseline normal; >1.5 - 3.0 x baseline if baseline abnormal
2. AST/ALT: >5.0 to 20.0 x ULN, if baseline normal; >5.0 - 20.0 x baseline, if baseline abnormal; bilirubin:>3.0 - 10.0 x ULN if baseline normal; >3.0 - 10.0 x baseline if baseline abnormal
3. AST/ALT: >20.0 x ULN, if baseline normal; >20.0 x baseline, if baseline abnormal; bilirubin: >10.0 x ULN if baseline normal; >10.0 x baseline if baseline abnormal
4. The decision to withhold or permanently discontinue pembrolizumab is at the discretion of the investigator or treating physician. If control achieved or ≤ Grade 2, pembrolizumab may be resumed. .
5. Events that require discontinuation include but are not limited to: encephalitis, and other clinically important irAEs (eg. Vasculitis and sclerosing cholangitis).

[figure not shown]

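### Table 5, general instruction 2 omits a negation: as printed, reaching a low corticosteroid dose within 12 weeks requires permanent discontinuation of pembrolizumab

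*Protocol*

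**What the plan says.** Table 5 opens with four general instructions for immune-related adverse events (irAEs).

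- Instruction 2: "Pembrolizumab must be permanently discontinued if AE does not resolve or the corticosteroid dose is" ≤10 mg/day "within 12 weeks of the last pembrolizumab treatment".
- Instruction 3: "The corticosteroid taper should begin when the irAE is" Grade 1 or lower, and the taper lasts at least 4 weeks.
- Instruction 4: "If pembrolizumab has been withheld, pembrolizumab may resume after the irAE decreased to" Grade 1 or lower, following the steroid taper.

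Four event rows combine withholding with an ordered taper. The pneumonitis and diarrhea/colitis rows say "Administer corticosteroids (initial dose of 1 to 2 mg/kg prednisone or equivalent) followed by taper". The Grade 2 AST/ALT/bilirubin row says "Administer corticosteroids (initial dose of 0.5 to 1 mg/kg prednisone or equivalent) followed by taper". The nephritis row says "Administer corticosteroids (prednisone 1 to 2 mg/kg or equivalent) followed by taper".

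The paragraph in Section 6.5.2 on restarting study interventions defers to the table: "If the toxicities do resolve and conditions are aligned with what is defined in" Table 5, the combination may be restarted at the investigator's discretion. If the toxicity does not resolve, or the criteria for resuming are not met, the subject comes off all study interventions.

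**The concern.** Instruction 2 has two conditions. The first is negated (the event does not resolve). The second has its own subject and verb and carries no negation, so it is met when the steroid dose is low. A low dose after recovery is the result the taper is meant to produce, and instruction 4 treats it as grounds for resuming.

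Two errors follow from a literal reading. A subject who recovers and tapers on time must stop pembrolizumab for good. If the site then regards the resume criteria as unmet, the restart paragraph takes the subject off belantamab mafodotin as well. In the other direction, a recovered subject still on more than 10 mg/day at week 12 is not stopped by the steroid condition. Section 6.12.4 expects that repeated tapering courses may be needed, so prolonged steroid use is a realistic case.

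This is a mandatory rule on permanent discontinuation, and Section 7 allows no waivers except for immediate safety concerns.

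**Working it through.** No sample size, power or error-rate figure is involved. The check compares the printed instructions case by case and then asks how readily the conflict arises.

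**1. The rule as printed, as corrected, and instruction 4**

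| Status | Instruction 2 as printed | Instruction 2 with negation | Instruction 4 |
|---|---|---|---|
| irAE resolved, taper done, dose ≤10 mg/day within 12 weeks | must stop | no stop | may resume |
| irAE resolved, dose still >10 mg/day at week 12 | no stop | must stop | not yet, taper unfinished |
| irAE not resolved | must stop | must stop | not met |

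The printed and corrected rules differ in both resolved cases, and in each the printed action is the reverse of the corrected one. Only the first row is a direct contradiction with instruction 4. In the second row, instruction 4 still blocks re-dosing, so what is lost is the explicit dose threshold and the 12-week limit.

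**2. Which side of 10 mg/day disqualifies elsewhere**

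Exclusion criterion 23 (Section 5.2) bars chronic systemic steroid doses above 10 mg daily of prednisone equivalent. Instruction 2 as printed points the opposite way.

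**3. Does a normal taper reach the printed stop range?**

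Inputs: the starting doses in the four rows; body weight 42 to 130 kg, which Section 2.2.5.1 gives for the earlier belantamab mafodotin studies and is assumed to apply here; and mg/kg read as a daily dose.

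- Grade 2 AST/ALT/bilirubin row: 0.5 × 42 = 21 mg/day up to 1 × 130 = 130 mg/day.
- Pneumonitis, diarrhea/colitis and nephritis rows: 1 × 42 = 42 mg/day up to 2 × 130 = 260 mg/day.
- Weight at which the lowest starting dose equals 10 mg/day: 10 / 0.5 = 20 kg.

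Every starting dose is above 10 mg/day at realistic adult weights, so a taper completed within the window must pass into the printed stop range. With the minimum 4-week taper, this covers any subject who begins tapering by week 12 − 4 = 8 after the last pembrolizumab dose.

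**4. How much of the table is involved**

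Table 5 has 12 event rows:

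- 4 order withholding, steroids and a taper;
- 5 make steroids depend on severity or clinical indication (hypophysitis, neurological, myocarditis, exfoliative skin conditions, all other irAEs);
- 3 order no steroids (type 1 diabetes/hyperglycemia, hyperthyroidism, hypothyroidism).

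4 + 5 + 3 = 12. The hypophysitis wording could also be read as making only the hormone replacement conditional.

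**5. Is the rule corrected elsewhere?**

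No other section restates it. The restart paragraph and Section 6.12.4 both send the reader back to Table 5.

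**The case against.** The strongest reply is that the literal rule cannot be operated, so nobody would follow it. A subject on no steroid has a dose of 0 mg/day and, with 21-day cycles, is normally within 12 weeks of the last pembrolizumab dose. Read without context, the rule would stop nearly everyone, against a plan of up to 35 cycles. Once the irAE context is read in, that same context supplies the missing word. Other text points the same way: instruction 4 allows resumption, and the permanent stops for recurrent Grade 2 pneumonitis and recurrent Grade 3 colitis presuppose re-exposure after a first event. This stands as a reason to think harm unlikely. It does not make the printed rule right, and the protocol nowhere states it correctly.

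Three narrower points also stand, as limits on the consequences:

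- A taper that first reaches 10 mg/day after week 12 does not meet the printed trigger. The conflict is confined to tapers completed inside the window.
- Loss of belantamab mafodotin is not automatic. It requires the site to let instruction 2 override instruction 4.
- The dose arithmetic shows where the texts collide. It does not measure any effect on subjects.

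**Conclusion.** The concern holds. The steroid condition in instruction 2 is the reverse of what instruction 4 requires, and it gives the wrong action for a subject who recovers and tapers within 12 weeks. It should be fixed because it is a binding discontinuation rule, even though most readers of all four instructions together would probably infer the intent.

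The number of subjects affected cannot be estimated from the protocol. The ORR test and the sample size are not affected. The conclusion rests on the sign in instruction 2 being ≤, as it reads; the same sign makes sense where it stands in instructions 3 and 4. The dose range also rests on the weight assumption, but with break-even at 20 kg that assumption is not critical.

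**What to change.** In Table 5, instruction 2, replace the steroid condition with: *the corticosteroid dose has not been reduced to 10 mg/day or less of prednisone or equivalent*. Keep the 12-week limit and punctuate the sentence so that it plainly applies to both conditions. Naming prednisone or equivalent is a small addition that matches the event rows and exclusion criterion 23.

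Leave the wording on resolution of the event unchanged. Footnote 4 lets some events (type 1 diabetes/hyperglycemia, Grade 3 or 4 hypophysitis) resume on control or at Grade 2 or lower, and redefining resolution as Grade 1 would create a new conflict.

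The medical monitor should confirm the intended wording. The cost is one corrected sentence and a letter to sites.

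### Table 5, All Other irAEs: the recurrence term in the permanent-discontinuation cell has no effect, so a recurrent Grade 3 event has no automatic stop

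*Protocol*

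**What the plan says.** Table 5 of the Protocol sets the pembrolizumab action for each immune-related event. Its last row, All Other irAEs, has three levels. Persistent Grade 2 is withheld. Grade 3 is "Withhold or discontinue based on event". Permanent discontinuation applies to "Recurrent Grade 4 or Grade 4". Note 5, attached to the Grade 3 action, says: "Events that require discontinuation include but are not limited to: encephalitis, and other clinically important irAEs". Its list is open and does not mention recurrence.

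Two other rows carry a recurrence clause. Pneumonitis stops permanently at "Recurrent Grade 2, Grade 3 or 4", and diarrhea/colitis at "Recurrent Grade 3 or Grade 4".

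Under Attribution of Toxicity in Section 6.5.2, both drugs are held on the Table 5 criteria whichever drug the investigator blames, so the row bears on the whole regimen.

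**The concern.** A recurrence clause exists to make a second event count for more than a first. Here it cannot, because the first Grade 4 event already ends treatment. The cell differs by one digit from the diarrhea/colitis cell, where the clause does work, and this suggests a slip in the grade.

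The row covers every immune-related event that the table does not name. If a recurrent Grade 3 stop was meant, it is missing from the rule. A patient could have a Grade 3 event, recover, restart both drugs and have the same Grade 3 event again without the table requiring a stop.

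**Working it through.** No arithmetic applies beyond counting rows. The check compares the cells and then looks for a rule elsewhere that would supply the missing stop.

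**Step 1, the logic of the cell.** The stop set is {Grade 4} together with {recurrent Grade 4}. The second lies inside the first, so the union is {Grade 4} and the recurrence term is redundant. With the diarrhea/colitis wording the set would be {Grade 4} plus {recurrent Grade 3}, and the clause would act.

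**Step 2, the rows side by side.**

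| Table 5 row | At a first Grade 3 event | Recurrence clause |
|---|---|---|
| Pneumonitis | stop | recurrent Grade 2, operative |
| Diarrhea/colitis | withhold | recurrent Grade 3, operative |
| AST/ALT/bilirubin | stop | none |
| T1DM/hyperglycemia | withhold | none |
| Hypophysitis | withhold or stop | none |
| Hyperthyroidism | withhold or stop | none |
| Hypothyroidism | continue | none |
| Nephritis | stop | none |
| Neurological | stop | none |
| Myocarditis | stop (from Grade 2) | none |
| Exfoliative | ungraded: withhold if suspected, stop if confirmed | none |
| All Other | withhold or stop, by event | recurrent Grade 4, inoperative |

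**Step 3, the counts.**
- Rows: 12. Continue only: 1 (hypothyroidism). Withholding possible: 12 − 1 = 11.
- With a recurrence clause: 3, of which 2 are operative and 1 is not. Without one: 11 − 3 = 8.
- Of those 8, 5 stop at or before the first Grade 3 event or on confirmation (AST/ALT/bilirubin, nephritis, neurological, myocarditis, exfoliative). The other 3 are endocrine (T1DM/hyperglycemia, hypophysitis, hyperthyroidism).
- Rows in which treatment may resume after Grade 3: diarrhea/colitis, the 3 endocrine rows and All Other, so 5. One of the 5 stops on a recurrent Grade 3 event. With the endocrine rows set aside, 5 − 3 = 2 remain: diarrhea/colitis, which stops on recurrence, and All Other, which does not.

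In both operative clauses the recurrence grade is one below the lowest grade that stops treatment outright: 2 against 3 for pneumonitis, and 3 against 4 for diarrhea/colitis. In All Other it is 4 against 4.

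**Step 4, other text that might supply the stop.**
- Note 5 sorts Grade 3 events by type, not by episode.
- Table 5 general instruction 2 turns on non-resolution or steroid dose within 12 weeks. General instruction 4 allows resumption at Grade 1 or less after taper. Neither counts episodes.
- Section 6.5.2, Restarting Study Interventions, lets the investigator restart the combination once the toxicity resolves and the Table 5 conditions are met.
- Section 6.5.1 has a general rule for toxicities outside Tables 4 and 5: withhold at Grade 3 or above, and resume at Grade 1 or less with Medical Monitor agreement. It has no recurrence stop.
- Section 5.4 ends treatment for unacceptable toxicity and allows stopping at the investigator's discretion. The only recurrence it names is Grade 2 pneumonitis.

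None of these makes a recurrent Grade 3 event in the All Other row a mandatory stop.

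**The case against.** The strongest reply is that the instruction can be followed as printed: Grade 4 means stop, and Grade 3 means a decision by event. The diarrhea/colitis row is also an imperfect comparator. Its Grade 3 action is a plain withhold, so a stop there needs its own clause, whereas the All Other Grade 3 cell already allows discontinuation at the first event. In that respect it resembles hypophysitis and hyperthyroidism, which have no recurrence clause. Of the 5 rows that permit resumption after Grade 3, 4 lack a recurrence stop, and the contrast narrows to 1 of 2 only once the endocrine rows are set aside, a grouping the table does not itself use. A stray recurrence word would explain the cell as well as a wrong digit would.

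Most of this stands. It limits what can be said about intent, and it means that the absence of a recurrence stop is not by itself evidence of error. It does not rescue the term, which is redundant on any reading.

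A reader might go further and infer that recurrent Grade 3 events are ungoverned, or that sites may restart as they please. The documents do not support that. Each event needs a withhold-or-discontinue decision under note 5, resumption has conditions, and Section 5.4 applies. If the Section 6.5.1 rule is read to reach these events, restarting also needs the Medical Monitor's agreement. Whether it does is open, since that rule covers toxicities not listed in the tables and the All Other row arguably lists them.

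**Conclusion.** The point holds as a minor safety-wording error. That the recurrence term is inoperative is certain from the text as printed. It follows that a recurrent Grade 3 event in the catch-all row has no automatic stop, only the discretionary controls above. The size is one digit in one cell, 1 of 12 rows.

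A reader might also infer that the sponsor certainly meant recurrent Grade 3. The Protocol does not say so. It is an inference from the two operative clauses and the one-digit difference, held with medium confidence, and it assumes that the digit is the one in the source table. ORR, the DLT rules, and the safety and futility boundaries are unaffected.

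**What to change.** Check the cell against the source table and ask the sponsor which rule was intended.

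- If a recurrence stop was intended, change the cell to "Recurrent Grade 3 or Grade 4". This costs one digit on paper but adds a mandatory stop, so some patients with a second Grade 3 event would have to leave treatment who might otherwise have continued after review.
- If none was intended, delete the recurrence words so that the cell reads Grade 4 only. This leaves the working rule unchanged.

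The cell should be edited in either case.
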